15.2 Secondary Endpoints

15.2.1 Conversion to AD

Conversion to AD is measured by NINCDS-ADRDA and NIA [14] criteria for diagnosis of Alzheimer Disease and Clinical Dementia Rating (CDR) (Appendix A).

Kaplan-Meier survival curves will be estimated and will plot the proportion of treatment and control subjects who remain without a diagnosis of AD at month 24, 36, 48, and 60. The log-rank test will be used to determine whether the survival curves are different for the two groups of subjects. Cox proportional hazards will be used to assess the incidence of AD in treatment versus control subjects adjusting for age and sex.

15.2.2 Cognitive change

The CDR-SB, MMSE, and ADAS-cog are administered at baseline and at months 4, 8, 12, 16, 20, 24, 36, 48, and 60. Separate linear mixed-effects modeling will be used to compare differences in the scores on each these tests using all available observations. Treatment (IVIG/placebo), MCI status (early, late), and treatment X MCI status will be fixed factors and the respective baseline score will be included as the continuous covariate. For statistically significant ($p < 0.05$), interactions, MCI status will be stratified and the analyses will be conducted for each stratum.

Data will be analyzed to assess safety after 25 subjects complete three months of follow-up. Safety will be evaluated through documentation of adverse events. Appropriate safety data summaries will be provided to the DSMC after each interim analysis.

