2.4 Secondary endpoints

- Conversion from a-MCI to AD as measured by NINCDS-ADRDA, National Institute on Aging (NIA) criteria for diagnosis of Alzheimer Disease, [14] and Clinical Dementia Rating (CDR)
- Change in ventricular volume as measured by MRI at baseline, 12 months, 24 months, 36 months, 48 months, and 60 months following infusion of either 0.4 g/kg NewGam or 0.9% saline solution (placebo) every 14 days x 5 in patients with positive CSF A β 1-42/CSF P-Tau_{181P} Alzheimer signature
- Change in cognitive performance between baseline and 4, 8, 12, 16, 20, 24, 36, 48, and 60 months after the first infusion as measured by: Alzheimer Disease Assessment Scale-cognitive subscale (ADAS-cog)
- Mini Mental State Exam (MMSE)
- Clinical Dementia Rating (CDR) and Sum of Boxes (CDR-SB)

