3.3 Estimated study duration

The duration of each study subject is approximately 24 months, including one screening visit over a period of approximately 28 days, 5 days of infusions over a 2-month period of time, and follow-up visits at 4, 8, 12, 16, 20, and 24 months after the first infusion. Subjects will be given the option to continue study follow-up visits at 36, 48, and 60 months after the first infusion.

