8.0 CONVERSION TO ALZHEIMER DISEASE

Patients who convert to AD will have the choice of remaining in the study on a modified follow-up visit schedule, or may withdraw from the study. Depending on when the conversion occurs, the subjects will be asked to complete the following:

- Complete all Visit 7 study activities described above
- Complete only the following for Visit 8:

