 1. HIV-I & II, HCV, HBV, B19, HAV
 2. Adverse events and Concomitant Meds
- Complete all Visit 9 study activities described above
- Subjects will not attend Visit 10 and Visit 11
- Complete all Visit 12 study activities
- Complete all Visit 13, 14, and 15 study activities (optional)

Patients who convert to Alzheimer Disease will be followed for safety reasons, to determine rate of conversion between groups, and to track any continued changes in ventricular volume between the 0.4 g/kg NewGam or 0.9% saline solution (placebo) groups.

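### The cognitive mixed model in 15.2.2 lists no visit or treatment-by-visit term, so its treatment effect has no defined time point and depends on who attends the optional extension

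*Combined protocol and SAP*

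**What the plan says.** Section 2.4 sets the cognitive endpoint for each of ADAS-cog, MMSE and CDR-SB as "Change in cognitive performance between baseline and 4, 8, 12, 16, 20, 24, 36, 48, and 60 months after the first infusion". Section 15.2.2 analyses them as follows: "Separate linear mixed-effects modeling will be used to compare differences in the scores on each these tests using all available observations". It then lists the model terms: "Treatment (IVIG/placebo), MCI status (early, late), and treatment X MCI status will be fixed factors and the respective baseline score will be included", with baseline as a continuous covariate. If the treatment by MCI-status interaction has p<0.05, the analysis is repeated within each MCI stratum.

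No visit, time, treatment-by-visit, random-effect or covariance term is named, and no target month. Nothing elsewhere in the current text supplies one. Sections 15.1, 15.2.1 and 15.2.3 do name the months of their comparisons.

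Two other sections determine which scores exist. Section 3.3 makes the later visits voluntary: "Subjects will be given the option to continue study follow-up visits at 36, 48, and 60 months after the first infusion". Under section 8.0, subjects who convert to AD "will have the choice of remaining in the study on a modified follow-up visit schedule, or may withdraw from the study". For those who stay, the instruction "Complete only the following for Visit 8" leaves only virology, adverse events and concomitant medication, so there are no cognitive tests at month 8. Months 16 and 20 are dropped ("Subjects will not attend Visit 10 and Visit 11"), while month 24 is kept ("Complete all Visit 12 study activities").

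**The concern.** A repeated-measures model with no time term gives one treatment effect, or one per MCI stratum, pooled over visits. It cannot report a difference at any of the nine months in 2.4, and it cannot separate the 24-month objective in 2.1 from the 36-, 48- and 60-month objectives in 2.2.

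The pooled effect also depends on attendance. These subjects are expected to decline, so those with later visits have worse average scores for that reason alone. If one arm sends more subjects into the extension, the model has no term to absorb the passage of time and attributes the difference to treatment. The visit mix depends on outcome as well, because section 8.0 removes some tests after conversion.

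Section 17.0 says the two-year results may lead to expansion of the study or a larger trial. A cognitive estimate tied to no time point would be weak input to that decision.

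**Working it through.** The plan gives no numerical figure for the cognitive model, so there is none to reproduce. Its 82% power in 16.0 concerns ventricular volume.

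**1. Inputs.** From the documents: the visit months (2.4), 25 subjects per arm (16.0), conversion of 15% and 20.8% per year and a 42% lower risk after IVIG (1.0), and the visit rules in 3.3 and 8.0. Assumed, because the documents do not give them: within-subject correlation ρ of 0.3 to 0.8, rate of decline, extension attendance, and the extra decline of converters.

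**2. Mean month of a subject's scores.**
- Stops at month 24: (4+8+12+16+20+24)/6 = 14.0.
- All nine visits: 228/9 = 25.33.
- Converter diagnosed at month 4 who stays: (4+12+24)/3 = 13.33, or 184/6 = 30.67 with the extension.

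**3. What the single coefficient represents.** If the arms diverge linearly, it is 14/24 = 58% of the month-24 difference when nobody enters the extension and 25.33/24 = 106% when everyone does. A simulation with a true month-24 difference of -2.0 agrees. On months 4 to 24 the listed model gave -1.18 with all visits attended and -1.00 under the section 8.0 rules. With the extension it gave -1.49 to -1.86, depending on who continued. Adding visit and treatment-by-visit gave -1.89 to -2.08 at month 24 in all these cases.

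**4. No drug effect, unequal attendance.** Assume both arms decline by 0.3 SD a year, with extension attendance of 80% in one arm and 40% in the other. The spurious difference is (0.3/12) × (25.33 - 14.0) × (0.80 - 0.40) = 0.113 SD, against the arm that attends more. Mixed-model fits on large simulated samples gave 0.108 to 0.117 SD without a visit term and 0.006 SD or less with one. The standard error of the average over months 4 to 24 is 0.124 to 0.163 SD (step 6), so the shift is 0.113/0.163 = 0.7 to 0.113/0.124 = 0.9 standard errors. It is proportional to the attendance gap: 60% against 50% gives 0.028 SD, and equal attendance gives zero.

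**5. Section 8.0.** With P(m) = 1 - (1-r)^(HR × m/12), month 8 is cancelled if conversion is diagnosed by month 4, month 16 if by month 12, and month 20 if by month 16. Cancelled sessions per arm are 25 × (P4 + P12 + P16).
- Placebo: 25 × (0.0527+0.1500+0.1948) = 9.94 at r = 0.15, and 25 × (0.0748+0.2080+0.2672) = 13.75 at r = 0.208. Of 150 planned sessions this is 6.6% and 9.2%.
- IVIG at HR 0.58: 5.97 and 8.39, or 4.0% and 5.6%.

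Through month 24, with all converters staying, this cuts the conversion-driven part of the arm difference by about 11 to 27%. That is 0.05 to 0.11 standard errors for a 1 SD converter decline and about 0.1 to 0.2 for 2 SD. Through month 60 the shift runs from about a 5% cut to a 15% inflation.

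**6. Cost of a month-24 contrast.** Baseline-adjusted, 25 per arm, in SD units:
- Average over months 4 to 24: √[(2/25)(ρ + (1-ρ)/6 - ρ²)] = 0.162, 0.163 and 0.124 at ρ = 0.3, 0.5 and 0.8.
- Month 24: √[(2/25)(1-ρ²)] = 0.270, 0.245 and 0.170.
- Ratio: 1.67, 1.50 and 1.36.

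Under linear divergence the month-24 difference is 24/14 = 1.71 times the average, so its signal to noise is 1.03 to 1.26 times that of the average. If the effect is constant from month 4, it is 0.60 to 0.73 times.

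**The case against.** **An average may be intended.** Sections 2.1 and 2.2 speak of efficacy over a period, and 2.4 singles out no month. A covariate-adjusted average over follow-up is a legitimate target, and the 58% in step 3 compares two different quantities. This stands: a reader might infer that the coefficient is biased because it falls short of the month-24 difference, but 15.2.2 never says it estimates that difference. The objection does not rescue an average whose visits are set by voluntary attendance.

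**A time term may be implied.** The section is brief and the analyst may intend one. But it itemises the model down to an interaction and a covariate, and a literal reading omits time.

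**Section 8.0 hardly matters.** A reader might infer that the cancelled tests bias the comparison against IVIG. The documents do not support that. The shift is small against the standard error, has no fixed sign once the extension is included, and creates no difference when conversion and attendance are equal between arms. Section 32.2 also reports no year-1 and one year-2 conversion in early MCI, so in that stratum almost nothing is cancelled.

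**Month 24 alone may cost power.** Section 1.0 reports MMSE gains of 2.5 at 6 months and 0.5 at 18, against an expected loss of 1.5 per 6 months. The differences from expectation are 2.5 + 1.5 = 4.0 and 0.5 + 4.5 = 5.0, which is nearly constant. Extrapolated, that is 5.5 at month 24 and 4.67 on average over months 4 to 24, a ratio of 1.18. Dividing by 1.36 to 1.67 gives signal to noise of 0.71 to 0.86. Those were open-label AD patients on longer dosing, but the point stands: month 24 should not be imposed as the sole comparison.

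**Covariance.** Nine visits with an unstructured covariance need 9 × 10/2 = 45 parameters from 50 subjects, so the structure must be chosen and stated.

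**Conclusion.** The point holds. As written, 15.2.2 gives a treatment effect with no defined time point, although the endpoint in 2.4 is defined by month, and the effect is confounded with time if extension attendance differs between arms. The size depends on that gap: about 0.11 SD, or 0.7 to 0.9 standard errors, at an assumed 0.3 SD yearly decline and 80% against 40% attendance, falling to zero at equal attendance. The documents give no attendance figures, so unequal attendance is a risk, not an established fact. Section 8.0 is a minor addition of about 0.05 to 0.2 standard errors under assumed converter declines. These are secondary endpoints in a study the protocol calls exploratory, so severity is modest.

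**What to change.** Amend 15.2.2 so that:
- categorical visit and treatment-by-visit are fixed effects beside the terms already listed;
- the within-subject covariance is stated, in a form that 50 subjects can support;
- all available observations are still used;
- the model-based treatment difference is reported at month 24 and as the equally weighted average over months 4 to 24, with months 36, 48 and 60 supportive;
- one of the first two is named in advance as the lead comparison;
- the treatment by MCI-status check uses that same contrast.

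No extra data are needed; the cost is a few sentences and a choice of covariance. Which contrast leads is the sponsor's choice. Month 24 fits the study horizon, and section 8.0 keeps that visit for converters who stay, but its standard error is about 1.4 to 1.7 times that of the average and it loses power if the effect is constant. The average is more precise but less specific in time.

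The change does not fully repair the loss from converters who withdraw. If a quarter leave after diagnosis, the month-24 contrast still loses 5 to 18% of the conversion-driven difference, against 16 to 43% for the single average, under the assumptions above.

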4.1 Inclusion criteria

1. Signed and dated written informed consent obtained from the subject in accordance with the local regulations. The subject's collaborative informant must also consent to participate in the study.
2. Age from 50 to <85 years.

3. Diagnosis of Mild Cognitive Impairment, Amnesic type (single or multi domain) according to Petersen criteria (Appendix B), NIA diagnostic guidelines, [15] and supported by a CDR score of 0.5.
4. Mini-Mental State Examination (MMSE) score of 24-30, inclusive.
5. Rosen Modified Hachinski Ischemic score ≤ 4 .
6. Willing to consent to ApoE testing and agree to disclose ApoE4 status. Previous ApoE testing will be accepted.
7. Receiving stable doses of medication(s) for the treatment of non-excluded medical condition(s) for at least 30 days prior to screening.
8. Agree to refrain from taking any medication, vitamin, or herbal supplement indicated for a-MCI or AD or considered to enhance cognition unless approved by the investigator for the duration of the study.
9. Ability to attend all clinical visits and have an informant capable of accompanying the subject on specific clinic visits for two years or the duration of the study.
10. The subject's collaborative informant (support person) must be someone who has known the subject for at least 4 years; agrees to have at least 2 separate communications with the study participant per month for the duration of the study (one of these communications must be in person); and attends and completes the CDR interview at 8 study visits along with the subject.
11. Fluency in English and evidence of adequate premorbid intellectual functioning.
12. Adequate manual dexterity, visual, and auditory abilities to perform all aspects of the cognitive and functional assessments.
13. Venous access suitable for repeated infusion and phlebotomy.
14. In the opinion of the investigator, the subject and informant will be compliant and have a high probability of completing the study, including all scheduled evaluations and required tests.

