7.1 VISIT 1: Screening

The following screening procedures will occur up to 28 days prior to Visit 2 (Day 1) infusion:

- Obtain signed and dated SHCIRC approved written Informed Consent from the subject and collaborative informant prior to the initiation of any screening procedure
- Assess Inclusion/Exclusion criteria
- Obtain medical history
- Record prior medications
- Assess Petersen criteria for mild cognitive impairment
- Determine Rosen Modified Hachinski Ischemic score
- Record vital signs
- Perform physical examination including height and weight
- Perform neurological examination
- Obtain standard 12-lead ECG
- Obtain a brain MRI according to Appendix E for clinical assessment, ventricular volume, and review the scan for evidence of vasogenic edema, microhemorrhage, infarction or other clinically significant abnormality
- Perform lumbar puncture to obtain CSF A β 1-42/CSF P-Tau_{181P}
- Administer MMSE, ADAS-Cog, and CDR-SB
- Obtain blood sample for ApoE genotyping, IgA deficiency, serum viscosity

- Obtain blood sample for complete blood count (CBC) and comprehensive metabolic panel (chemistry panel). (Appendix D)
- Obtain blood sample for thyroid stimulating hormone (TSH), vitamin-B12 and rapid plasma reagin laboratory tests
- Obtain blood sample for HIV-I & II, HCV, HBV, B19, HAV
- Obtain urine sample for routine urinalysis

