15.0 STATISTICAL ANALYSIS

15.1 Primary endpoint

The aim of the primary efficacy analysis is to demonstrate an advantage for subjects treated with IVIG over subjects treated with placebo at the end of the study as measured by change in ventricular volume. The primary efficacy analyses will be performed on the intent-to-treat (ITT) population. The ITT population is defined as all subjects who were randomized, received three or more infusions, and had a brain MRI at baseline and at 24 months.

Annualized percent change in total ventricular volume (APCV) is the primary biomarker of interest. Brain MRI will be obtained at baseline, 12 months, 24 months, 36 months, 48 months, and 60 months. Differences between the IVIG and placebo group at month 12, 24, 36, 48, and 60 will be analyzed using a 2 x 2 analysis of variance. Participants will also be classified as early MCI (EMCI) if baseline CDR-SB is less than 1.5, and late MCI (LMCI) if CDR-SB is greater than or equal to 1.5.

Treatment (IVIG, placebo), MCI status (EMCI, LMCI), and the treatment X MCI status interaction will be included in the model. If the interaction is statistically significant ($p < 0.05$), MCI status will be stratified and differences in APCV between the groups compared within each stratum.

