22.0 APPENDIX C

22.1 Schedule of study activities

Study Visit	1	2	3	4	5	6	7	8	9	10	11	12	13	14	15
Study Time Point	Day -28 To Day -1	D1	D14	D28	D42	D56	M4	M8	M12	M16	M20	M24 /ET ⁶	M36	M48	M60 /ET ⁷
Visit Type (Visit Window)	Screening	Infusion Visits (±1 day)					Follow-up (±7 days)					Follow-up (±14 days)			
CLINICAL															
Informed consent	X														
Inclusion/Exclusion	X	X													
Medical Hx/Prior/Baseline Medications	X														
a-MCI Petersen/NIA criteria review	X														
Modified Hachinski Ischemia Scale	X														
ApoE4 genotyping ¹	X														
Vital Signs	X	X	X	X	X	X	X	X	X	X	X	X	X	X	X
Physical Exam	X	√ ²					X	X	X	X	X	X	X	X	X
Neurological Exam	X	√ ²					X	X	X	X	X	X	X	X	X
ECG	X						X					X			
Brain MRI	X								X			X	X	X	X
CSF-amyloid protein 1-42 tau 181P biomarker mixture (Optional)	X														
Mini Mental State Exam (MMSE)	X						X	X	X	X	X	X	X	X	X
CDR-SB, ADAS-cog	X						X	X	X	X	X	X	X	X	X
HIV-I & II, HCV, HBV, B19 ³ , HAV ³	X						X	X							
IGA deficiency	X														
Serum viscosity	X														
CBC, Chemistry Panel (Appendix B)	X						X		X			X			
TSH, Vit-B12, RPR ⁴	X														
Urinalysis ⁵	X														
Adverse events & Concomitant Meds		X	X	X	X	X	X	X	X	X	X	X	X	X	X

Study Visit	1	2	3	4	5	6	7	8	9	10	11	12	13	14	15
Study Time Point	Day -28 To Day -1	D1	D14	D28	D42	D56	M4	M8	M12	M16	M20	M24/ ET ⁶	M36	M48	M60 /ET ⁷
Visit Type (Visit Window)	Screening	Infusion Visits (±1 day)					Follow-up (±7 days)					Follow-up (±14 days)			
THERAPY															
Randomization		X													
Infusion of IVIG or placebo		X	X	X	X	X									
Assess infusion site		X	X	X	X	X									
¹ Previous ApoE4 testing will be accepted				⁴ RPR required if not done in the last 12 months prior to screening											
² Exams may occur within 72 prior to infusion				⁵ Urine culture may be performed if indicated											
³ Performed at 4 and 8 months only if subject is negative at baseline				⁶ Early Termination visit for subjects in the two study (Section 7.13)											
				⁷ Early Termination visit for subjects in the three year extension study (Section 7.13)											

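### ApoE4 status is known for every subject before randomisation but enters no section 15 model; prespecifying it as a covariate would be a cheap, modest improvement if it is prognostic

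*Combined protocol and SAP*

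**What the plan says.** Inclusion criterion 6 in section 4.1 makes the genotype a condition of entry: "Willing to consent to ApoE testing and agree to disclose ApoE4 status". Section 7.1 collects it at screening ("Obtain blood sample for ApoE genotyping, IgA deficiency, serum viscosity"), and a footnote to the schedule in Appendix C allows an existing result instead ("Previous ApoE4 testing will be accepted"). Either way the value is fixed before randomisation and should be complete. The CSF marker, by contrast, is labelled optional in Appendix C, yet it has its own analysis in 15.2.3.

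The section 15 models are:

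- **15.1, annualised percent change in ventricular volume (APCV):** "Treatment (IVIG, placebo), MCI status (EMCI, LMCI), and the treatment X MCI status interaction will be included in the model".
- **15.2.1, Cox model for conversion to AD:** treatment against control, "adjusting for age and sex".
- **15.2.2, mixed models for CDR-SB, MMSE and ADAS-cog:** "Treatment (IVIG/placebo), MCI status (early, late), and treatment X MCI status will be fixed factors". The only other term that this section names is each test's own starting value: "the respective baseline score will be included as the continuous covariate".
- **15.2.3, CSF-signature subset:** no covariate named.

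ApoE4 appears in none of them, and no reason is given. Section 5.1 describes 1:1 allocation under a scheme that the research scientist will develop, and names no stratification factor. Sections 3.1 and 16 give 25 subjects per arm.

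**The concern.** A baseline variable that is measured in everyone and fixed before randomisation can validly be used as a covariate. If it predicts the outcome beyond what is already in the model, leaving it out has two consequences. Its share of the outcome variance stays in the residual. And when it falls unevenly between arms, the observed treatment difference moves with it. With 25 per arm and no balancing described, a noticeable imbalance is quite possible.

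There is also a practical side. If the arms turn out to differ in ApoE4 carriage and the plan is silent, any later adjustment will look post hoc. Section 17 lets a trend at two years support expansion or a larger trial, so a small shift in the estimate could carry some weight.

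**Working it through.** **Inputs from the documents.** 25 per arm; two-sided alpha 0.05; 82% power for a 120-unit difference in ventricular volume (section 16). No SD is stated. No power, SD or effect size is stated for any cognitive endpoint.

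**Assumptions, none in the documents.** Carrier share 40% to 60%; carriers decline 0.3 to 0.6 SD more than non-carriers; partial R² of ApoE4, given the existing model terms, from 0 to 0.10.

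**Step 1: the plan's own figure.** The 82% can be neither confirmed nor refuted without an SD. Solving backwards with the normal approximation, the standardised effect is (1.960 + 0.915) × √(2/25) = 0.813, so the SD is 120/0.813 = 147.6 units. With the t distribution these become 0.830 and 144.6. The 82% serves below only as a reference point, because it belongs to the primary endpoint.

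**Step 2: precision.** The existing cognitive model is treated as an analysis of covariance with 5 parameters (intercept, treatment, MCI status, interaction, baseline score). Residual degrees of freedom are 45 before and 44 after adding ApoE4. Allowing for the expected cost of chance covariate imbalance,

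variance ratio = (1 − R²) × (45 − 1)/(44 − 1) = (1 − R²) × 1.023.

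New power = Φ(2.875/√ratio − 1.960).

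| Partial R² | Variance ratio | 82% becomes |
|---|---|---|
| 0 | 1.023 | 81.1% |
| 0.02 | 1.003 | 81.9% |
| 0.05 | 0.972 | 83.1% |
| 0.10 | 0.921 | 85.0% |

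Break-even is 1 − 43/44 = 0.023, or about 0.02. With 40 analysable subjects it is 1 − 33/34 = 0.029, or about 0.03. This is a single-time-point approximation to the repeated-measures model of 15.2.2.

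**Step 3: consistency of the two assumed ranges.** A carrier effect d with carrier share p implies R² = d²p(1 − p). At p = 0.5, d = 0.3 gives 0.0225 and d = 0.6 gives 0.09. The assumed effect range therefore corresponds to about 2% to 9% of variance, which is a gain from nil to about 3 points.

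**Step 4: chance imbalance.** For two independent Binomial(25, p) counts, the probability that the arms differ by at least 5 carriers (20 percentage points) is 0.193 at p = 0.4, 0.203 at p = 0.5 and 0.193 at p = 0.6. Fixing the total at 20, 25 or 30 carriers among 50 gives 15% to 26%. A gap of exactly 5 shifts an unadjusted difference by (5/25) × 0.3 = 0.06 SD up to (5/25) × 0.6 = 0.12 SD. The standard error of a 25-against-25 difference is √(2/25) = 0.283 SD, so the shift is 0.06/0.283 = 0.21 to 0.12/0.283 = 0.42 of one standard error.

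**Step 5: the Cox model.** Section 1.0 cites conversion of about 15% and 20.8% a year. By month 24 that is 50 × (1 − 0.85²) = 13.9 to 50 × (1 − 0.792²) = 18.6 events if treatment has no effect. With treatment, age and sex there are 4.6 to 6.2 events per coefficient. A fourth coefficient takes that to 3.5 to 4.7.

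**The case against.** The strongest reply is that the premise lies outside the documents. They never say that ApoE4 is prognostic, give no effect size, and do not say why it is collected. If it adds nothing beyond baseline score and MCI status, the extra term costs about a point of power. That stands, and it makes the benefit conditional.

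A reader might infer that the cognitive models are shown to lose precision. They are not: below a partial R² of about 0.02 the covariate does not pay for itself.

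A reader might also infer that an ApoE4 imbalance would bias the trial and go wholly uncorrected. Neither follows. Chance imbalance under randomisation is already allowed for in the unconditional type I error, and baseline score and MCI status absorb whatever part of an ApoE4 imbalance they carry. Nor do the documents establish that allocation is unstratified. Section 5.1 leaves the scheme undescribed, so the most one can say is that no stratification is stated.

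Finally, it may be said that this is a preference among covariates in secondary analyses of a study that calls itself exploratory. That is fair as to priority. Against it, the plan already adjusts for baseline factors, the value is already in hand for everyone, and a choice made in advance is easier to defend than one made after an imbalance is seen.

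**Conclusion.** The point holds as a conditional, low-priority improvement. ApoE4 status is an entry requirement and is known before randomisation, but section 15 neither uses it nor explains its omission, and no stated stratification would balance it.

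The size is modest. On the 82% reference, adjustment ranges from a loss of about 1 point (no prognostic value) to a gain of about 3 points (partial R² of 0.10). A carrier gap of 5 or more arises in roughly one trial in five, and a gap of 5 moves the difference by less than half a standard error. These figures rest on the assumed carrier share, carrier effect and R², and on a power figure borrowed from the primary endpoint.

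The omission contradicts nothing in the documents, invalidates no test and misstates no figure. The case does not extend to the Cox model, where 14 to 19 expected events by month 24 make a fourth coefficient a real trade-off.

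**What to change.** In 15.2.2, prespecify ApoE4 carrier status (no allele against at least one) as a fixed factor in each of the three cognitive mixed models. In 15.1, add the same factor to the APCV model. State that it is a covariate only, with no ApoE4 interaction and no ApoE4 subgroup test. Leave the age and sex adjustment in 15.2.1 unchanged, with ApoE4 at most in a sensitivity analysis of the Cox model. If the investigators do not regard ApoE4 as prognostic beyond baseline score and MCI status, a sentence saying so would serve instead.

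The cost is a sentence in each of the two sections, one degree of freedom per model, and about 1 power point if ApoE4 turns out not to be prognostic. No new data are needed.
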